9. STATISTICAL CONSIDERATIONS

Statistical summaries will be descriptive in nature and will be reported separately for each part of the study within the clinical study report (CSR). All study participants who are randomized to receive placebo in Part 1 will be pooled as a respective placebo control group for Part 1. Placebo from Part 2a and Part 2b will be pooled separately.

9.1 STATISTICAL HYPOTHESES

No statistical hypothesis testing is planned for this study.

9.2 SAMPLE SIZE DETERMINATION

The sample size was determined by practical considerations and not based on statistical power calculations. In Part 1, approximately 40-50 participants will be enrolled in four to five cohorts of 10 participants each (eight to receive RO7239958 and two to receive placebo). In Part 2, approximately 28-49 CHB patients will be enrolled in *four* to seven arms of seven participants each (six to receive RO7239958 and one to receive placebo). Part 2a will include approximately 28-35 participants in *four to* five arms. Part 2b will include approximately 14 participants in two arms.

9.3 POPULATIONS FOR ANALYSES

For the purpose of analysis, the following populations are defined in [Table 11](#).

Table 11 Analysis Populations

Population	Description
Safety	All study subjects who have received at least one dose of the study medication, whether prematurely withdrawn from the study or not, will be included in the safety analysis.
Pharmacokinetic	Study subjects will be excluded from the PK analysis population if they significantly violate the inclusion or exclusion criteria or deviate significantly from the protocol, or if data are unavailable or insufficiently complete to allow the analysis. Excluded cases will be documented together with the reason for exclusion. All decisions on exclusions from the analysis will be made prior to database closure.
Efficacy	The analyses of viral dynamic response in Part 2a (and potentially Part 2b) of the study will include all patients who were randomized and received at least one dose of study drug (RO7239958 or placebo) and with at least one post-treatment assessment. Participants will be analyzed according to the treatment group to which they are randomized.

9.4 STATISTICAL ANALYSES

9.4.1 Demographics and Baseline Characteristics

Descriptive statistics will be used for demographic and baseline disease characteristics as applicable for each part of the study. These will include for Part 1 and Part 2 age, gender, race, ethnicity, country of origin, weight, height, body mass index; and for Part 2 only, HBV baseline characteristics (e.g., HBsAg levels) and HBV history (e.g., duration of HBV diagnosis HBV treatment history, fibrosis status), and where measurable (participants with detectable HBV RNA), the viral genotype. All study participants who are randomized to receive placebo will be pooled as respective placebo control groups, according to each part of the study.

For continuous variables, mean, standard deviation, median, and minimum and maximum values will be presented. For categorical data, the proportion of study participants in each category will be summarized.

9.4.2 Safety Analyses

All safety analyses will be based on the entire safety analysis population (see [Table 11](#)).

The objectives of the safety analyses are to assess the safety and tolerability of RO7239958 compared to placebo after single SC ascending doses in healthy participants and multiple SC ascending doses in CHB patients.

Participants randomized to receive RO7239958 will be analyzed by cohort or arm. All study subjects who are randomized to receive placebo will be pooled as respective placebo control groups, according to each part of the study (See Section 9).

The safety data, including AEs, ISRs, reason for withdrawal from study, laboratory data, ECG, concomitant medications, vital signs, and physical examination results will be listed and summarized descriptively. Marked abnormalities of laboratory data will be flagged. As appropriate, listings, summary tables and graphs (participant plot and/or mean plots) will be provided to describe safety and tolerability assessments.

Table 12 Safety Statistical Analysis Methods

Endpoint	Statistical Analysis Methods
Adverse events	The original terms recorded on the eCRF by the Investigator for adverse events will be coded by the Sponsor. Adverse events will be summarized by mapped term and appropriate thesaurus level.
Clinical laboratory tests	All clinical laboratory data will be stored on the database in the units in which these were reported. Laboratory test values will be presented in International System of Units (SI units; Système International d'Unités) by individual listings with flagging of abnormal results. Summary tables of change from baseline over time will be displayed. Shifts in NCI CTCAE grades v5.0 from baseline to the worst grade observed during treatment will be presented for selected laboratory parameters. See Appendix 4 for details on standard reference ranges and data transformation and the definition of laboratory abnormalities.
Vital signs	Vital signs data will be presented by individual listings with flagging of values outside the normal ranges and flagging of abnormalities. In addition, tabular summaries will be used, as appropriate.
ECG data analysis	For the analyses of ECG data, see Section 8.2.3 .
Concomitant medications	The original terms recorded on the participants' eCRF by the Investigator for concomitant medications will be standardized by the Sponsor by assigning preferred terms. Concomitant medications will be presented in summary tables and listings.

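### The safety summaries group participants by randomised treatment and there is no as-received rule, so anyone given the wrong product would be misclassified in the descriptive safety tables

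*Combined protocol and SAP*

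**What the plan says.** Section 9.4.2 sets the groups for every safety summary. For active treatment: "Participants randomized to receive RO7239958 will be analyzed by cohort or arm". For control: "All study subjects who are randomized to receive placebo will be pooled as respective placebo control groups, according to each part of the study". Section 9 uses the same basis for Part 1 ("All study participants who are randomized to receive placebo in Part 1 will be pooled as a respective placebo control group for Part 1") and splits the Part 2 controls ("Placebo from Part 2a and Part 2b will be pooled separately").

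In Section 9.3, the safety row of Table 11 defines membership by dosing ("All study subjects who have received at least one dose of the study medication, whether prematurely withdrawn from the study or not") and says nothing about which treatment group a member is counted in. The efficacy row of the same table does address grouping, and states that patients are analysed as randomised. No rule for grouping by treatment received appears anywhere in the document.

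The stopping criteria in Section 4.1.3 work differently. They count healthy participants (out of eight) or patients (out of six) who receive RO7239958.

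**The concern.** A safety population defined by dosing is normally paired with grouping by what was given. Here the two are separated. A placebo-randomised participant who is given RO7239958 enters the safety population and is then summarised under placebo. In the reverse case, an unexposed participant is summarised under an active cohort or arm.

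Safety compared with placebo is the primary objective (Section 3, Table 7), and Section 9.1 plans no hypothesis test, so the descriptive tables are the primary result. With groups this small, one misplaced participant visibly changes an incidence.

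The event is also one that the protocol foresees. Doses are weight-based and placebo is sodium chloride supplied by the site (Table 10). Each dose is prepared at the site by a qualified individual (Sections 6.2 and 6.4). Section 5.2 of Appendix 2 names administration of a wrong drug among the medication errors to be recorded. The plan says how such an error is reported but not how the participant is then analysed.

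**Working it through.** **1. The plan's own sizes.** For the healthy-volunteer part, Section 9.2 states that "approximately 40-50 participants will be enrolled in four to five cohorts of 10 participants each (eight to receive RO7239958 and two to receive placebo". It gives Part 2 as arms of seven, six active and one placebo.

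- Part 1: 4 × 10 = 40 to 5 × 10 = 50
- Part 2 overall: 4 × 7 = 28 to 7 × 7 = 49
- Part 2a: 4 × 7 = 28 to 5 × 7 = 35
- Part 2b: 2 × 7 = 14

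All four agree with the stated figures.

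**2. Pooled placebo groups.** Size = cohorts or arms × placebo participants in each, pooled as Section 9 directs. The share of one exposed participant is 1/n.

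| Part | Placebo n | Share of one exposed participant | Placebo n if grouped as received |
|---|---|---|---|
| 1 | 4 × 2 = 8 to 5 × 2 = 10 | 1/8 = 12.5% to 1/10 = 10% | 7 to 9 |
| 2a | 4 × 1 = 4 to 5 × 1 = 5 | 1/4 = 25% to 1/5 = 20% | 3 to 4 |
| 2b (optional) | 2 × 1 = 2 | 1/2 = 50% | 1 |

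In the reverse error, one unexposed participant is 1/8 = 12.5% of a Part 1 active cohort or 1/6 = 16.7% of a Part 2 active arm.

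**3. Effect on a reported incidence.** Suppose one placebo-randomised participant in Part 1 receives RO7239958 and has the only event.

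- As randomised: placebo 1/8 = 12.5% (or 1/10 = 10%), active cohort 0/8.
- As received: placebo 0/7 (or 0/9), active cohort 1/9 = 11.1%.

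The same case in Part 2b at planned size, if the participant is counted as active:

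- As randomised: placebo 1/2 = 50%, active arm 0/6.
- As received: placebo 0/1, active arm 1/7 = 14.3%.

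**4. Over-enrolment.** Section 5.5 accepts up to two extra patients per Part 2 arm and does not state their allocation. Assuming 0 to 2 extra placebo patients per arm, the Part 2b placebo group ranges from 2 to 2 × 3 = 6, and the share from 50% down to 1/6 = 16.7%. Two is therefore the size at planned enrolment, not a fixed value.

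**5. Single and repeated dosing.** Part 1 gives one dose, so a dispensing error there is a clean swap. In Part 2a a participant can receive up to five doses (Section 4.1), and Part 2b treatment can run to Day 85 (Section 4.1.1). One wrong dose there gives mixed exposure, which a bare as-received rule does not classify.

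**The case against.** The strongest reply is that the Section 9.4.2 sentences are about display: active shown by cohort or arm, placebo pooled by part. Similar pooling language appears in Section 9 and for demographics in Section 9.4.1, and none of it mentions a misdosed participant. Where the authors wanted an as-randomised rule they wrote one, in the efficacy row of Table 11, and they left it out of the safety row. A reader might infer that the plan deliberately adopts an as-randomised safety analysis. The documents do not establish that intent, and the wording may simply be loose. It is nevertheless the only grouping instruction given, and a programmer following it would group by randomisation.

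Three further points stand and limit the concern:

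- **Visibility.** Wrong-drug errors must be recorded and reported within 24 hours whether or not harm follows (Appendix 2, Section 5.2). Section 9.5 lists deviations and drug administration, and safety data are also listed individually. A recorded error would be seen. None of this moves the participant in the summary tables.
- **Stopping rules.** A reader might infer that escalation or arm stopping would be distorted. The documents do not support that, because the criteria in Section 4.1.3 already count participants who receive the drug. Section 6.3.2 allows aggregated reports by treatment group to reach those making dose decisions, but does not say that they follow the Section 9.4.2 grouping.
- **Likelihood.** No error is reported and no rate is given.

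**Conclusion.** The gap is real. Taken literally, Sections 9 and 9.4.2 would misclassify a participant given the wrong product in the primary-objective safety tables, and those tables would then disagree with the stopping criteria about who was exposed. One such participant would be 10–12.5% of the Part 1 placebo group, 20–25% of Part 2a and 50% of Part 2b.

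These figures assume planned enrolment and one error affecting a placebo-randomised participant who is then counted as exposed. A reader might take a placebo group of two as typical of the study. It arises only in Part 2b, which is optional and may be over-enrolled.

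This is a low-probability matter calling for a minor-to-moderate correction. It affects descriptive tables only; it does not affect stopping decisions or the individual listings.

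**What to change.** 1. In Section 9, Section 9.4.2 and the safety row of Table 11, replace grouping by randomised treatment with grouping by treatment actually received, including dose or regimen. Placebo pooling by part stays as it is.
2. Add an analysis rule for Part 2 participants with mixed exposure. One workable example: anyone who received at least one dose of RO7239958 is summarised with the active group for the dose received, with a footnote giving the assigned treatment and the doses affected.
3. Keep grouping as randomised for the Efficacy population.

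No separate listing of mismatches is needed if the drug administration listing in Section 9.5 shows assigned and received treatment together.

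The cost is a few sentences in three places and one decision on mixed exposure, best settled before unblinded safety summaries are produced. No extra data are needed, and nothing changes in the tables if no error occurs. A clinical statistical analysis plan appears in the abbreviation list but is not among the documents; if it already holds such a rule, the protocol text should be aligned with it.

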9.4.2.1 ECG Data Analysis

ECG data will be presented by individual listings with flagging of values outside the normal ranges and flagging of marked abnormalities. Summary descriptive statistics for the actual values and changes from baseline will be tabulated by nominal time for HR, QRS duration, PR and QTcF. For multiple measurements taken at a nominal time-point, the average of these measurements will be used as the value at that nominal time-point in all summaries. In addition, QTcF will be categorized at each time-point as ≤ 450 msec, $> 450-480$ msec, $> 480-500$ msec and > 500 msec and summarized. Similarly, a summary will be provided of the QTcF changes from baseline at each time-point categorized as < 30 msec, $30-60$ msec, and > 60 msec. Changes of the overall ECG interpretation, T-wave and U-wave morphology will be summarized. QTcF will be assessed by a central group.

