8.2.3 Electrocardiograms

Triplicate 12-lead ECG will be obtained as outlined in the SoA (see Section 1.3) using an ECG machine that automatically calculates the heart rate and measures PR, QRS, QTc intervals. ECGs will be collected after the participant has been in a supine position for at least 10 minutes prior to each ECG evaluation. At the specified time-points, 12-lead ECGs will be obtained in triplicate, i.e., three consecutive interpretable 12-lead ECGs within a 3-5-minute period, and recorded in the case report form (CRF). Triplicate recordings should be taken for any unscheduled ECG.

At each time-point at which triplicate ECGs are required, three individual ECG tracings should be obtained as closely as possible in succession, and the full set of triplicates should be completed in less than 5 minutes.

All ECG recordings must be performed using a standard digital high-quality, high-fidelity ECG machine equipped with computer-based interval measurements. Automated ECG intervals (PR [PQ], QRS, QT, QTcF [Fridericia's correction; to be derived in eCRF]) and heart rate (HR) will be captured or calculated, and the changes in T-wave and U-wave morphology will be documented. Changes in T-wave and U-wave morphology and overall ECG interpretation will be documented on the eCRF. T-wave information will be captured as normal or abnormal, U-wave information will be captured in two categories: absent/normal or abnormal.

The following are requirements for ECG assessments:

1. Digital ECG recordings, storage and analysis.
2. Three useful recordings must be collected without artefacts, per time-point.
3. Body position should also be consistently maintained for each ECG performed. In particular, changes in HR should be avoided. The absence of any environmental distractions (television, radio, conversation) during the pre-ECG rest and the ECG recording in the clinic must be emphasized.
4. Avoid ECG recordings within 3 hours after meals (it is accepted that this is not possible after the light breakfast which is administered prior to dosing in the fed period for the relevant cohort).
5. Strictly match timing and conditions of ECG recording to baseline. Conditions to be standardized include food intake, activity level, stressors, and room temperature.
6. If possible, the same machine, brand and model, should be used for the same study subject throughout the study.
7. ECGs should be 12-lead, recorded at 25 mm/sec for at least 10 seconds.

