8. In some cases, it may be appropriate to repeat abnormal ECGs to rule out improper lead placement as contributing to the ECG abnormality.
9. ECG machines should have periodic calibration and service records (minimum once a year).
10. If any QT/QTc values > 500 msec or increases from pre-dose on Day 1 QTc > 60 msec (as provided by the machine and read by the cardiologist), the site should repeat the ECG (triplicate) within the next 5 minutes and notify the Sponsor. If confirmed, ECG recordings should be repeated at least hourly until two successive ECGs show QTc values below the threshold value that triggered the repeated measurement.

For safety monitoring purposes, the Investigator or designee must review, sign, and date all ECG tracings. Paper or electronic copies will be kept as part of the participant's permanent study file at the site. If considered appropriate by Roche, ECGs may be analyzed retrospectively at a central laboratory.

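### QTcF outliers are summarised only by time-point: the plan does not say how repeat and unscheduled ECGs enter the tables, and it has no per-participant maximum

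*Combined protocol and SAP*

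**What the plan says.** ECG findings belong to the primary safety endpoint (Section 3, Table 7). Section 8.2.3 requires triplicates: "three individual ECG tracings should be obtained as closely as possible in succession". It asks for triplicates at any unscheduled ECG as well. Under its item 10, if any QT/QTc exceeds 500 msec, or QTc rises by more than 60 msec from Day 1 pre-dose, "the site should repeat the ECG (triplicate) within the next 5 minutes and notify the Sponsor". If the finding is confirmed, ECGs follow at least hourly until two in succession are below the triggering threshold.

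Section 9.4.2.1 sets out the analysis:

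- "Summary descriptive statistics for the actual values and changes from baseline will be tabulated by nominal time".
- "For multiple measurements taken at a nominal time-point, the average of these measurements will be used as the value at that nominal time-point"; the sentence goes on to apply this to every summary.
- "QTcF will be categorized at each time-point as" at most 450, above 450 to 480, above 480 to 500, and above 500 msec.
- "a summary will be provided of the QTcF changes from baseline at each time-point categorized as" below 30, 30 to 60, and above 60 msec.
- "ECG data will be presented by individual listings with flagging of values outside the normal ranges and flagging of marked abnormalities".

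Table 12 (Section 9.4.2) sends the reader to Section 8.2.3 for the ECG analysis, but that section holds no summary rule. The same table plans shifts to the worst on-treatment grade for selected laboratory parameters. Nothing comparable is planned for ECG.

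**The concern.** A categorical QTcF summary is there to show how many participants had a marked value. Three things stand in its way.

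1. The averaging sentence is not limited to the three recordings of a scheduled triplicate. A programmer could reasonably assign a repeat taken within 5 minutes to the same nominal time-point and average six recordings.
2. Hourly repeats and other unscheduled ECGs are given no place in tables laid out by time-point.
3. Counts per time-point cannot be added up into a count of participants.

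The groups are small: eight on active drug per Part 1 cohort and six per Part 2 arm (Section 9.2). One participant is therefore 1/8 = 12.5 or 1/6 = 16.7 percentage points.

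**Working it through.** The plan gives no figure on this point to reproduce. All QTcF readings below are assumed; the cut-offs and ECG times are the plan's.

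**1. What pooling would do, if it is intended.** Let m1 be the mean of the scheduled triplicate and m2 the mean of the repeat. The six-recording mean is (m1 + m2)/2, which is at most 500 when m2 ≤ 1000 − m1.

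| m1 (msec) | Pooled value is ≤ 500 if m2 is at most |
|---|---|
| 501 | 499 |
| 505 | 495 |
| 510 | 490 |
| 520 | 480 |

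- Not confirmed: 508/505/502 (mean 505.0), then 485/490/488 (mean 487.7). Pooled: 2978/6 = 496.3, so the category falls from above 500 to above 480 to 500.
- Confirmed: 508/505/502, then 503/504/506 (mean 504.3). Pooled: 3028/6 = 504.7, category unchanged. In general, if m1 and m2 both exceed a threshold, so does their average.
- Change from baseline: 66 then 50 msec gives 116/2 = 58, so above 60 becomes 30 to 60.
- Triggered by one recording: 506/488/490 has mean 1484/3 = 494.7. The scheduled value is already below 500 before any repeat.

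**2. How often pooling would hide a true exceedance.** Assume independent normal triplicate means with SD 5 to 8 msec. The probability that the pooled mean is ≤ 500, given a first mean above 500, is:

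| True QTcF (msec) | Probability |
|---|---|
| 502 | 13% to 17% |
| 505 | 3% to 8% |
| 510 | 0% to 2% |

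**3. Where hourly repeats would fall.** Part 1 (Table 2) schedules post-dose ECGs over the first 24 hours at 1, 4, 8, 12 and 24 h. Of the 24 whole hours, 24 − 5 = 19 have no scheduled ECG. On the Part 2 full-profile days, Days 1 and 29 (Table 4), the times are 1, 4 and 8 h, so 8 − 3 = 5 of the first 8 hours have none.

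**4. Can an unscheduled peak change an outlier count?** A rise above 60 msec with QTcF still at or below 500 requires a baseline below 500 − 60 = 440 msec. Entry allows QTcF up to 450 msec (Section 5.2), so this is the ordinary case: for any baseline below 440, the change trigger is reached before the 500 trigger. Suppose it is met at 1 h and confirmed, and hourly ECGs follow. A value above 500 at 2 or 3 h that has come down by 4 h has no row. The participant appears under change above 60 msec, but never under QTcF above 500 msec.

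**5. Counting participants.** Part 1 has ten scheduled post-dose ECG times (1, 4, 8, 12 and 24 h; Days 8, 15, 22, 43 and 85). Suppose three of those rows each show one of eight active participants above a cut-off. That is one person three times (1/8 = 12.5%), three people once each (3/8 = 37.5%), or something between. In a Part 2 arm, the same three rows mean anything from 1/6 = 16.7% to 3/6 = 50%. Only a per-participant maximum separates these cases.

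**The case against.** A reader might infer that the averaging rule necessarily biases outlier counts downward. The documents do not support that. The natural reading is that the rule concerns the planned triplicate: Section 8.2.3 asks for three usable recordings per time-point and treats unscheduled ECGs as separate sets, and Section 8.2.2 uses the mean of three replicates for blood pressure and pulse rate. Pooling is neither stated nor excluded. Even if repeats were pooled, two triplicate means above a threshold cannot average below it. Where the true QTcF is 500 msec or less, pooling moves a chance exceedance back into its correct category, so nothing true is lost. Also, item 10 is triggered by any machine-provided QT/QTc value, not by a triplicate-mean QTcF, so the probabilities above only approximate the real process.

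On unscheduled ECGs, the objection is that hourly recordings follow only a confirmed finding, so the participant is normally already in the outlier category that set them off. This holds for that threshold when both triplicate means exceed it. It does not hold for a higher one, as in step 4 of the working. That such ECGs have no row is inferred from the table layout, not stated, and some could coincide with scheduled times.

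It is also true that the data are not lost. Flagged individual listings are planned, the Sponsor is notified, new clinically relevant findings are reported as adverse events (Section 7.1), and QTcF is assessed centrally. The study is descriptive, and with six or eight on active drug per group a careful reader can go through the listings. That limits the problem to the summary tables. It neither settles the averaging rule nor supplies the count of participants.

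**Conclusion.** The point holds as a gap in the summary tables and is a cheap improvement. The plan does not define how the repeat triplicate is handled. Its tables give no evident place to unscheduled ECGs, and they cannot yield the number of distinct participants who ever exceeded 480 or 500 msec or a change of 60 msec.

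The participant-count problem needs no assumption about pooling. In the example it is the difference between 12.5% and 37.5% of a Part 1 cohort's active participants. The dilution problem is conditional: it requires pooling and a repeat that does not confirm. It is small once the true value is clearly above the cut-off (3% to 8% at a true 505 msec, under the assumed normal model with SD 5 to 8 msec and independent triplicates). The unscheduled-peak problem rests on the table layout and can change a count when a change trigger at or below 500 msec is followed by a value above 500 between scheduled times.

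**What to change.** In Section 9.4.2.1, state that:

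- averaging applies to the three recordings of one triplicate;
- the scheduled triplicate is the value at the nominal time-point;
- repeat triplicates are not merged with it.

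Add one table by treatment group giving each participant's maximum post-dose QTcF and maximum change from baseline. Use scheduled and unscheduled triplicate means and the existing categories.

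The cost is a few lines of text and one extra table, with no new data or procedure. The drawback is that maxima are somewhat inflated by chance and by the extra ECGs that a high reading sets off, so outlier counts may look slightly less favourable. A footnote saying so, with the by-time-point tables kept alongside, would be enough.
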